6.3.3.2 Remote Walk Speed Test Administration

Previous studies have shown the feasibility of a home-administered walk test. A self-administered, adapted 6 minute walk time (6MWT) test (the HomeHeart-Walk) had a strong intra-class correlation coefficient (0.98) with a standard in person 6 MWT.^{72,73} The test was well

received by participants who had a median age of 64 (range: 49 — 80) years old.⁷² The study concluded that self-administered walk test is a reliable and useful method of collecting physical activity data in a medically-challenged, older population.⁷² We will implement a similar approach and restrictions used in that study by excluding patients with documented new onset of heart failure, unstable angina pectoris, fever, complex arrhythmia, resting diastolic blood pressure of 100 mm Hg or more or unstable gait from performing the test on their own.⁷²

Subjects with documented new onset of heart failure, unstable angina pectoris, fever, complex arrhythmia, resting diastolic blood pressure of 100 mm Hg or more, or unstable gait will not be asked to perform the self-administered walk test. This should be ascertained via medical record review prior to contacting the subject to arrange a remote visit.

The walk speed test should be administered remotely as follows*:

1. Instruct the subject to lay out a 4 meter (13' 1") walking path using a measuring tape.
2. The subject will walk the 4 meter path twice at his or her usual pace.
3. For each walking trial, the amount of time (in seconds) will be recorded. The process by which the walk speed is recorded may be modified based on the circumstances of the remote visit. For example, if the entire walking path is in view of the coordinator, the coordinator may observe the walk test and record time. Alternatively, the subject may record the time (e.g., using the Stopwatch function on a cell phone) and report the results to the coordinator.

*Variations implemented to remotely conduct the walk speed test will be left to the discretion of the coordinator; however, the walk speed test should be administered twice using a 4 meter walking course (per section 6.3.1. of the protocol).

6.4 APPENDIX 4: SUBJECT/PATIENT REPORTED ASSESSMENTS AND SUBJECT/PATIENT REPORTED OUTCOMES (PRO)

The following table lists all subject reported assessments to be collected, including the number of items and estimated time to complete at each time point. This appendix also includes all items/questions included on each subject reported assessment. For some assessments, language has been modified to fit administration electronically or on paper, as opposed to in person. Any modifications are noted in the below sections.

| Study Assessments / Testing | # of items | Minutes | Baseline (≤21 days Pre-conditioning) | Day 100 -14/+21 | Day 180 +/- 28 | Day 365 +/- 28 |
|---|------------|---------|--------------------------------------|---------------------|----------------------|----------------------|
| Karnofsky performance status by subject | 1 | <1 | X | X | X | X |
| Facility admissions | 1-3 | 1 | | X | X | X |
| PROMIS Depression | 4-12 | 1-2 | X | X | X | X |
| PROMIS Anxiety | 4-12 | 1-2 | X | X | X | X |
| PROMIS Physical function | 4-12 | 1-2 | X | X | X | X |
| OARS IADL | 6 | 2 | X | X | X | X |
| Falls | 1 | <1 | X | X | X | X |
| Frailty phenotype: Weight loss | 2 | <1 | X | | X | X |
| Frailty phenotype: Exhaustion | 5 | 2 | X | | X | X |
| Frailty phenotype: Activity level | 6-18 | 2-5 | X | | X | X |
| Number of medications for polypharmacy | 4 | 1 | X | | | |
| Race/ethnicity, education, income, demographics | 6 | 2 | X | | | |
| Total time for Subject reported outcomes | | | 13-20 minutes | 7-10 minutes | 11-17 minutes | 11-17 minutes |

Race/ethnicity, education, income, demographics

1. What is the highest grade you finished in school?

- 1-8 grades
- 9-11 grades
- High school graduate
- Some post-college work
- Some college
- Junior college degree
- College degree (BA/BS)
- Advanced degree

2. What is your marital status?

- Single, never married

- Married
- Separated
- Divorced
- Widowed

3. What is your current employment status? (please choose all that apply)

- Employed 32 hours a week or more
- Employed less than 32 hours a week
- Full-time student
- Part-time student
- Homemaker
- On medical leave
- Disabled
- Unemployed
- Retired
- Other

4. What is your race? (please select all that apply)

- White
- Asian
- Black or African-American
- Native Hawaiian or Other Pacific Islander
- Native Indian or Alaskan Native
- Don't know

5. What is your ethnicity?

- Hispanic or Latino
- Not Hispanic or Latino
- Don't know

6. Please specify your household gross annual income. Include earnings by all family members living in your household, before taxes.

- Less than \$20,000
- \$20,000 - \$39,999
- \$40,000 - \$59,999
- \$60,000 - \$79,999
- \$80,000 - \$99,999
- \$100,000 or more

7. What the zip code of your primary residence?

Number of medications for polypharmacy

1. Are you taking any medications?

- Yes
- No

2. If yes, how many prescribed medications are you taking on a daily basis?

- ___ medications

3. How many over the counter medications are you taking on daily basis?

- ___ medications

4. How many herbs and vitamins are you taking on a daily basis?

- ___ herbs and vitamins

Karnofsky performance status from patient

1. Which of the following phrases best characterizes you at this time? (Please select one response)

- Normal, no complaints, no symptoms of disease
- Able to carry on normal activity, minor symptoms of disease
- Care for self, unable to carry on normal activity or to do active work
- Require occasional assistance but able to care for most of personal needs
- Require considerable assistance for personal care
- Disabled, require special care and assistance
- Severely disabled, require continuous nursing care

OARS IADL

1. Can you use the telephone...

- Without help, including looking up and dialing;
- With some help (*can answer phone or dial operator in an emergency, but need a special phone or help in getting the number or dialing*); or
- Are you completely unable to use the telephone?

2. Can you get to places out of walking distance...

- Without help (*can travel alone on busses, taxis, or drive your own car*);
- With some help (*need someone to help you or go with you when traveling*); or
- Are you unable to travel unless emergency arrangements are made for a specialized vehicle like an ambulance?

3. Can you go shopping for groceries or clothes (assuming you have transportation)...

- Without help (*taking care of all shopping needs for yourself, assuming you have transportation*);
 - With some help (*need someone to go with you on all shopping trips*); or
 - Are you completely unable to do any shopping?
4. Can you prepare your own meals...
- without help (*plan and cook full meals yourself*);
 - with some help (*can prepare some things but unable to cook full meals yourself*); or
 - are you completely unable to prepare any meals?
5. Can you do your housework...
- without help (*can clean floors, etc.*);
 - with some help (*can do light housework but need help with heavy work*); or
 - are you completely unable to do any housework?
6. Can you take your own medicines...
- Without help (*in the right doses at the right time*);
 - With some help (*able to take medicine if someone prepares it for you and/or reminds you to take it*); or
 - Are you completely unable to take your medicines?
7. Can you handle your own money...
- Without help (*write checks, pay bills, etc.*);
 - With some help (*manage day-to-day buying but need help managing your checkbook and paying your bills*); or
 - Are you completely unable to handle money?

Falls in past 6 months

Question has been modified from text box, to multiple choice response in order to control data entry in electronic format.

1. How many times have you fallen in the last 6 months?
- 0 times
 - 1 time
 - 2 times
 - 3 or more times

Facility admissions

At day 100 and 180

1. Have you been admitted to a skilled nursing facility in the last 3 months? This would include an acute rehabilitation facility, nursing-home, or sub-acute rehabilitation. Do NOT include admissions to the hospital.

- Yes
- No
- unsure

At day 365

1. Have you been admitted to a skilled nursing facility in the last 6 months? This would include an acute rehabilitation facility, nursing-home, or sub-acute rehabilitation. Do NOT include admissions to the hospital.

- Yes
- No
- unsure

Frailty phenotype: Weight loss*

Questions have been modified for electronic and paper administration during which patient may not be able to self-weigh or recall exact previous weights. Also modified to remove “Refused” response item, as patients may skip question to refuse.

At Pre-HCT

1. To the best of your knowledge, have you lost or gained weight over the past year?

- Yes
- No
- Don't know

2. [if yes] Did you lose or gain weight because you were trying to, or not (For example, by dieting or exercising)?

- Tried to
- Did not try to
- Don't know

Frailty phenotype: Exhaustion*

Questions have been modified to remove “Refused” response item, as patients may skip question to refuse.

* <https://www.johnshopkinssolutions.com/solution/frailty/>

* <https://www.johnshopkinssolutions.com/solution/frailty/>

1. In the past month, on average have you been feeling unusually tired during the day?

- Yes
- No
- Don't know

2. If yes, have you been feeling unusually tired:

- All of the time
- Most of the time
- Some of the time
- Don't know

3. In the past month, on average, have you felt unusually weak?

- Yes
- No
- Don't know

4. If yes, have you been feeling weak:

- All of the time
- Most of the time
- Some of the time
- Don't know

5. Using the scale below, would you please rate your usual energy level on a scale from 0 to 10 where 0 is no energy and 10 is the most energy that you have ever had. Please give a number between 0 and 10 that describes your usual energy level while awake in the last month?

No energy Most energy
0 1 2 3 4 5 6 7 8 9 10

Frailty phenotype: Activity level*

Questions have been modified for electronic administration and to remove "Refused" response item, as patients may skip question to refuse.

1. During the past two weeks have you walked for exercise?

- Yes
- No

* <https://www.johnshopkinssolutions.com/solution/frailty/>

- Don't know
2. If yes, how many times in the past two weeks have you walked for exercise?
- _____ times
3. If yes, what is the average amount of time you spent each time you walked for exercise?
- ___ hours
 - ___ minutes
4. During the past two weeks have you done moderately strenuous household chores, like scrubbing and vacuuming?
- Yes
 - No
 - Don't know
5. If yes, how many times in the past two weeks have you done moderately strenuous household chores?
- _____ times
6. If yes, what is the average amount of time you spent each time did moderately strenuous household chores?
- ___ hours
 - ___ minutes
7. During the past two weeks have you done moderately strenuous outdoor chores, like raking or mowing the lawn, shoveling snow, or working in the garden?
- Yes
 - No
 - Don't know
8. If yes, how many times in the past two weeks have you done moderately strenuous outdoor chores?
- _____ times
9. If yes, what is the average amount of time you spent each time you did moderately strenuous outdoor chores?
- ___ hours
 - ___ minutes
10. During the past two weeks have you been dancing?
- Yes
 - No
 - Don't know

11. If yes, how many times in the past two weeks have you been dancing?

- _____ times

12. If yes, what is the average amount of time you spent each time you have been dancing?

- ___ hours
- ___ minutes

13. During the past two weeks have you been bowling?

- Yes
- No
- Don't know

14. If yes, how many times in the past two weeks have you been bowling?

- _____ times

15. If yes, what is the average amount of time you spent each time you have been bowling?

- ___ hours
- ___ minutes

16. During the past two weeks have you been participated in any regular exercise program, such as stretching or strengthening exercises, swimming or any other regular exercise program?

- Yes
- No
- Don't know

17. If yes, how many times in the past two weeks have you participate in any regular exercise program?

- _____ times

18. If yes, what is the average amount of time you spent each time you have participated in any regular exercise program?

- ___ hours
- ___ minutes

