2.4.7 Data Capture of Subject-reported Evaluations

Table 4.2.4 summarizes subject clinical assessments over the course of the study. At the Pre-transplant time point, CIBMTR staff will provide site staff with a link to the electronic PRO instrument and a PDF of a paper version. Site staff will administer the PRO electronically or on paper, per subject request. If the PRO is done on paper, site staff will securely email or fax the completed instrument to CIBMTR to be entered into the electronic PRO (ePRO) system. At post-transplant time points, CIBMTR staff will administer the subject reported instruments electronically, or on paper upon subject's request. The number of questions and expected time burden for the subject may vary based on method of delivery. Additionally, each time point has a different number of assessments. The pre-transplant assessment will take 13-20 minutes to complete, the Day 100 will take 7-20 minutes, and the Day 180 and Day 365 will each take 11-17 minutes. The survey times vary based on method of delivery because computerized adaptive testing, used for participants who complete the survey online, has variable numbers of survey items given and time burden.

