3.2.2 Development/Progression of Frailty (DPF)

Frailty will be measured at baseline, day 100, day 180 and day 365 by the 5 component Hopkins frailty phenotype (5 points total, score of 3 or more is frail). Of note, weight loss at day 100, day 180 and 365 will be scored from the prior time point for the purposes of this study rather than 1 year weight loss. DPF at 1 year is defined as an increase to a score of 3 or more (i.e., frail) in subjects who are not frail at baseline, or an increase in the frailty score of one or more points in those who are already frail at baseline. Subjects who miss assessments will be considered censored at the date of last follow-up. Death prior to development/progression of frailty will be considered a competing risk.

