4.2.4 Subject Evaluations

Table 4.2.4 summarizes assessments over the course of the study.

Table 4.2.4: Study Assessments

| Study Assessments / Testing | Healthcare Team (H) or Subject Report (P) or Lab (L)* | Baseline (Pre-conditioning) | Day 100 - 14/+21 (abbreviated survey) | Day 180 +/- 28 | Day 365 +/- 28 |
|--|---|-----------------------------|---------------------------------------|----------------|----------------|
| Subject report | | | | | |
| Race/ethnicity, education, income, demographics | P | X | | | |
| Karnofsky performance status (KPS) by subject | P | X | X | X | X |
| PROMIS Physical function domain | P | X | X | X | |
| PROMIS Depression domain | P | X | X | X | X |
| PROMIS Anxiety domain | P | X | X | X | X |
| Facility admissions ³ | P | | X ⁵ | X ⁵ | X ⁵ |
| OARS IADL ¹ | P | X | X | X | X |
| Falls | P | X | X ⁵ | X ⁵ | X ⁵ |
| Frailty phenotype - Weight loss ² | P | X | X ⁵ | X ⁵ | X ⁵ |
| Frailty phenotype - Exhaustion ² | P | X | X | X | X |
| Frailty phenotype- Activity level ² | P | X | X | X | X |
| Number of medications for polypharmacy | P | X | | | |
| Healthcare team report | | | | | |
| Frailty phenotype - Walk Speed, 4 meter ² | H | X | X ⁷ | X ⁷ | X ⁷ |
| Frailty phenotype- Grip Strength ² | H | X | X | X | X |
| Montreal Cognitive Assessment (MoCA) for cognition | H | X | X ⁷ | | |
| CIBMTR Forms | H | X | X | X | X |
| Physician Prognostication Questionnaire | H ⁸ | X | | | |
| Early End of Study Questions (as needed) ⁶ | H | X | | | |
| Laboratory Testing | | | | | |
| CRP ⁴ | L | X | | | |
| Albumin ⁴ | L | X | | | |

*To be performed within 21 days prior to start of conditioning. If multiple values, enter value closest to conditioning.

- 1 OARS IADL 7 questions, omit “laundry” from Lawton IADL
- 2 Fried Frailty phenotype (5 point index). Subject report domains are weight loss, exhaustion and activity level and health care team reports walk speed and grip strength.
- 3 Overnight admission to any facility including nursing-home, subacute rehabilitation
- 4 Standard of care laboratory tests. Must be performed within 14 days prior to start of conditioning.
- 5 The time period for day 100 and day 180 questions will be the prior 3 months and at day 365 the prior 6 months.

- 6 For those who enroll but do not pursue transplantation
- 7 Assessment may be conducted remotely, as described in Appendix 6.3.3. if it is not feasible to conduct the assessment in-person.

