6.3.3 APPENDIX 3.3: REMOTE ADMINISTRATION OF FOLLOW-UP ASSESSMENTS

This study includes three assessments typically performed in-person at routine visits (Table 1). In-person testing at the time of a routine visit remains the preferred method of testing. However, when not feasible because the subject and/or research team will not be on site, the 4-meter walk and MoCA cognitive assessment can be performed remotely following previously validated methods in small non-HCT populations. Grip strength requires a dynamometer device and thus is not feasible to administer remotely. A protocol deviation will be reported for subjects who are unable to complete this assessment.

| Assessment | Timepoints | Proposed Change |
|--|----------------------------|--|
| Montreal Cognitive Assessment (MoCA) for cognition | Baseline, D100 | Site staff will administer MoCA by audio-visual teleconference. If AV conference is not available, a modified telephone version may be administered. |
| Frailty phenotype - Walk Speed, 4-meter | Baseline, D100, D180, D365 | Site staff will administer 4-meter walk test by audio-visual teleconference. If AV conference is not available, the subject may self-report results of the walk test by telephone. |
| Frailty phenotype- Grip Strength | Baseline, D100, D180, D365 | This assessment will be omitted from remote visits. |

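### Appendix 4 leaves three of the five frailty components out of the day-100 survey, while Table 4.2.4 and sections 2.4.8 and 3.2.2 require all five at that visit

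*Protocol*

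**What the plan says.** **Endpoint.** Section 3.2.2 says: "Frailty will be measured at baseline, day 100, day 180 and day 365 by the 5 component Hopkins frailty phenotype". Development or progression of frailty (DPF) is a rise to 3 or more points in subjects not frail at baseline, or a rise of at least one point in subjects already frail. Death first is a competing risk. Section 2.4.8 gives the same four time points and sets a three-month recall period for weight loss at day 100.

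**Schedule.** Table 4.2.4, which section 2.4.4 treats as the assessment schedule, marks weight loss, exhaustion and activity level at day 100; for example "Frailty phenotype - Exhaustion ² | P | X | X | X | X". It labels the day-100 column an abbreviated survey, yet its subject-report marks there are the same as at day 180.

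**Appendix 4 (section 6.4).** This table introduces itself as complete: "The following table lists all subject reported assessments to be collected". Its rows for the three self-reported components have an empty day-100 cell. The exhaustion row reads "Frailty phenotype: Exhaustion | 5 | 2 | X | | X | X", and the rows for weight loss and activity level show the same pattern, with marks at the other three visits only.

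It totals 7-10 minutes at day 100 and 11-17 minutes at days 180 and 365.

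**Section 2.4.7.** A third figure appears here: "the Day 100 will take 7-20 minutes".

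**Remote visits.** Appendix 3.3 says of grip strength: "This assessment will be omitted from remote visits".

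**The concern.** After transplant the registry's survey group administers the subject-reported instruments centrally (sections 2.4.7 and 4.2.5). The choice between the two tables is therefore made once and applies to every subject. Exhaustion asks about the past month and activity about the past two weeks, so answers not collected at day 100 cannot be recovered later.

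DPF is analysed by cumulative incidence and by a cause-specific Cox model across CHARM risk groups, with death as a competing event (section 5.8.2). Frailty is also summarised at each time point. A day-100 score built from fewer components and read against an unchanged threshold would miss early events. It would push detection to day 180 and record some subjects who became frail early and then died as deaths without DPF. Frailty trajectory by composite score is one of the stated hypotheses (section 2.2.1).

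**Working it through.** **Step 1: are the blank cells real?** The inputs are the Minutes column and the visit marks in the Appendix 4 table. An entry of <1 is taken as 0.5 minute (an assumption; 0 and 1 are shown as the range).

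Rows marked at day 100: Karnofsky <1, facility admissions 1, depression 1-2, anxiety 1-2, physical function 1-2, IADL 2, falls <1.
- Lower sum: 0.5 + 1 + 1 + 1 + 1 + 2 + 0.5 = 7.0
- Upper sum: 0.5 + 1 + 2 + 2 + 2 + 2 + 0.5 = 10.0

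The three frailty rows (weight loss <1, exhaustion 2, activity 2-5):
- Lower sum: 0.5 + 2 + 2 = 4.5
- Upper sum: 0.5 + 2 + 5 = 7.5

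| Survey | Recomputed, <1 as 0.5 | Range for <1 as 0 to 1 | Appendix 4 states |
|---|---|---|---|
| Day 100, frailty rows left out | 7.0-10.0 | 6-9 to 8-11 | 7-10 |
| Days 180 and 365, frailty rows included | 11.5-17.5 | 10-16 to 13-19 | 11-17 |
| Baseline | 13.5-19.5 | 12-18 to 15-21 | 13-20 |

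The stated day-100 total is reproduced without the three frailty rows. With them the total would match the day-180 figure. The empty cells are therefore part of the table as designed and not a fault of text extraction.

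The 7-20 minutes in section 2.4.7 fits neither survey. Its lower end is below the smallest total with the items (10), and its upper end is above the largest total without them (11).

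**Step 2: which components can be scored at day 100 under Appendix 4?**
- Walk speed: taken by staff, remotely if necessary.
- Grip strength: taken by staff, in person only.
- Weight loss: not in the survey. However, section 2.4.8 has staff measure weight and height, the Appendix 2 form records current weight at follow-up, and Appendix 3.1 lets BMI below 18.5 meet the criterion on its own.
- Exhaustion and activity level: no other source.

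**Step 3: compare the maximum score with the endpoint rules.** A subject not frail at baseline needs 3. A subject frail at baseline starts at 3 or more and needs at least 3 + 1 = 4.

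| Day-100 situation | Maximum score | Can reach 3? | Can reach 4? |
|---|---|---|---|
| Table 4.2.4, in person | 5 | yes | yes |
| Appendix 4, in person, with staff-form weight or BMI | 3 | only if all three are positive | no |
| Appendix 4, in person, walk and grip only | 2 | no | no |
| Appendix 4, remote, with reported weight | 2 | no | no |
| Appendix 4, remote, walk only | 1 | no | no |

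**Step 4: can the number of affected subjects be derived?** Table 5.9.2 gives survival at day 100 (88, 87, 84 and 81% by age group) and at one year (63, 61, 57 and 57%). The differences, 25, 26, 27 and 24 percentage points, cover days 100 to 365. No day-180 figure is given, nor any rate of new frailty by day 100. The number who become frail by day 100 and die before day 180 therefore cannot be computed.

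**The case against.** **The body text outweighs the appendix.** Table 4.2.4, section 2.4.8 and section 3.2.2 agree with each other, and one appendix grid differs. Nothing shows that the survey was built from Appendix 4. This stands, and it makes the harm conditional. It does not remove the contradiction, because Appendix 4 claims completeness and carries a time total calculated for the shorter survey.

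**A reader might infer that no subject can be classed as frail at day 100, with a ceiling of 2 of 5.** The documents do not support this. The ceiling of 2 assumes that weight loss comes only from the survey, whereas staff also record weight and height. In person, 3 points remain possible. The fallback is imperfect: the staff form looks back one year, while section 3.2.2 scores weight loss from the previous time point.

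**A reader might also infer that day-100 frailty is zero by construction, or that subjects frail at baseline would seem to recover.** Both readings require missing components to be scored as zero, which no passage says. Section 3.2.2 censors subjects who miss assessments, and section 2.4.8 assigns scoring centrally to the published algorithm. Handling of partial scores may properly sit in the analysis plan, which is not at hand. DPF also counts only increases, so apparent recovery is not an event.

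**Remote grip is disclosed.** Appendix 3.3 states the omission and requires a deviation report. That is fair, but it does not say how a four-component visit is compared with a five-component baseline.

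**Scale.** DPF is one of 10 secondary endpoints (section 5.8) and can still be detected at days 180 and 365. This stands.

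**Conclusion.** The contradiction is established. Appendix 4 omits three day-100 items that the schedule, the frailty section and the endpoint definition require, and its own time total confirms the omission.

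The consequence is conditional on the survey following Appendix 4. In that case:
- Two components, exhaustion and activity, cannot be scored at day 100.
- The maximum is 3 points in person and 2 at a remote visit without grip.
- A score of 3 requires every obtainable component to be positive, and progression to 4 or more cannot be shown.
- Much of DPF detection moves to day 180, and some early-frail subjects who die before then count as deaths without DPF. Their number is unknown.

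DPF would be delayed and under-ascertained, not lost. The one-year NRM endpoint and the candidate CHARM predictors, which are all measured at baseline, are untouched. The point deserves correction because the fix is small and the missed answers cannot be recovered.

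**What to change.** 1. Bring the Appendix 4 table and the day-100 duration in section 2.4.7 into line with Table 4.2.4, and confirm that the day-100 survey in use contains weight loss, exhaustion and activity level. The cost is a wording change, a survey correction if one is needed, and about 4.5-7.5 minutes once per subject. The day-100 survey would then take about as long as the day-180 one.
2. Add the day-100 weight-loss wording. Appendix 4 prints this question only for the pre-transplant visit. Reconcile the one-year look-back on the staff form with the interval in section 3.2.2.
3. If the items were not collected for some or all subjects, state that full DPF scoring starts at day 180 for them. This costs one sentence.
4. State that a sum over fewer components, including remote visits without grip, is not compared with the fixed threshold of 3 or with a five-component baseline score. Compare the same components at both times, or impute the missing one. The detail can go in the analysis plan.
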